2.10.2. Secondary Efficacy Assessments

2.10.2.1. DXA Scans

The total lean body mass, hip bone mineral density, total body mass and fat mass, appendicular lean body mass and bone turnover markers will be analyzed using an Analysis of Covariance model with baseline value as a covariate and treatment and region (country) as factors.

Observed values, percentage change, percent change from baseline and absolute change from baseline will be summarized using mean, standard deviation, coefficient of variation (CV%), median, minimum and maximum. A 95% confidence interval on the placebo adjusted change from baseline will also be presented.

The analysis of the values obtained from the central reader will be the primary analysis. The values obtained from the site (as recorded on the CRF) after applying a correction factor to adjust for the different DXA machine types will also be analyzed.

The definition of valid DXA from the central reader is as follows:

A valid DXA indicates the scan was acquired under the correct scanner setting, includes the entire region of interest and is free of artifacts that would affect quality results such as jewelry, surgical hardware, etc. Bioclinica technologists specifically trained on DXA scan analysis review the scans submitted to Bioclinica visually for those criteria as well as technical parameters such as scan mode, voltage setting, etc.

The initial concept behind the Month 3 analysis is that the subject would be on drug for at least 56 days and that the DXA measurement would be taken shortly (within 14 days) after the subject completed therapy. Thus, subjects who did not have at least 56 days of treatment or did not have their “Month 3” DXA within the allotted time was planned to be excluded from the analysis. It is important to note that the “Month 6” analysis is performed after the subject has been off therapy, so some of the data excluded from the Month 3 analysis will be included in the Month 6 analysis.

Given the variation of actual dosing and the timing of the actual DXA scan, there will be two definitions of a valid DXA for analysis purposes: “The Stringent Definition of Valid DXA” and “The Liberal Definition of Valid DXA”.

The stringent definition of valid DXA is as follows:

The subject must be on treatment for at least 56 days, have a valid baseline DXA and a DXA within 14 days after stopping treatment. (This is the definition as indicated in the protocol.)

The liberal definition of valid DXA is as follows:

The subject must have a valid baseline DXA and a DXA after baseline and prior to 98 days after starting treatment.

For the lean body mass measurements, the number and percent of subjects who had a 0.5kg, 1.0kg, 1.5kg and 2.0kg increase from baseline will be presented, and the number and percent of subjects who increased by 3% and number and percent of subjects who increased by 5% will also be presented.

Correlations and regression lines between total lean body mass (for both observed values and change from baseline) and the VK5211 PK concentration near Tmax and at trough levels will also be analyzed for each VK5211 treatment group and all VK5211 treatment groups combined. This analysis will be performed by visit and for all post-baseline visits combined.

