2.2. Study Populations

Safety Population:

All subjects who have taken a single dose of the study drug and provide follow-up information will be included in the safety population.

Intent-to-Treat (ITT) Population:

All subjects who have taken a single dose of the study drug and have a valid pre-baseline and post-baseline assessment will be included in the Intent-to-Treat population. Subjects will be analyzed as randomized, rather than as treated. This is the primary analysis population for assessing efficacy.

Per Protocol (PP) Population:

All Intent-to-Treat subjects who have taken at least 80% of the expected number of doses and do not have a major protocol violation will be included in the Per Protocol population. Subjects will be analyzed as treated, rather than as randomized.

Prior to unblinding, the exclusion of any subject from the Per Protocol Population will be documented including the reason for exclusion.

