2.10.1. Primary Efficacy Assessment

The absolute and percentage change in total body less head lean body mass at Visit 4 (Month 3) will be analyzed using an Analysis of Covariance model with baseline value as a covariate and treatment and region (country) as factors.

Observed values, percentage change and absolute change from baseline for all available visits will be summarized using mean, standard deviation, coefficient of variation (CV%), median, minimum and maximum. A 95% confidence interval on the placebo adjusted change from baseline will also be presented.

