2.11. Primary and Final Analyses

There are two planned analyses for the study: the primary analysis and the final analysis. The primary analysis is not an interim analysis. All subjects will have finished their treatment and the 12-week primary endpoints will be locked. Thus, the primary analysis is not subject to an alpha-spending penalty. No multiplicity adjustment is needed.

The primary analysis will be performed in a partially unblinded fashion. The generated tables will be presented using the actual treatment groups, but information pertaining to the unblinded treatment received by individual subjects will be blinded. So thus, the results will be known, but the individual subjects will still be blinded.

The primary analysis will be performed once all subjects have completed 3 months of treatment. The following variables will be included in the primary analysis:

Primary Objective

Percent Change in Total Body Less Head (TBLH) Lean Body Mass obtained from the DXA scan at 3 Months.

Secondary Objectives

Hip Bone Mineral Density (BMD) obtained from the DXA scan at 3 Months.

Total Lean Body Mass (TLBM) obtained from the DXA scan at 3 Months.

Appendicular Lean Body Mass (ALBM) obtained from the DXA scan at 3 Months.

Exploratory Objectives

6 Minute Walk Test

Short Physical Performance Battery (SPPB)

Short Form-36 (SF-36) Quality of Life Questionnaire

All analyses as indicated in the SAP will be presented for the final analysis.

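### The SAP does not say which of its two valid-DXA rules defines the primary Month 3 lean-mass analysis, and the stringent rule removes early stoppers from a table labelled Intent-to-Treat

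*SAP*

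**What the plan says.** Three parts of the primary analysis are settled.

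- **Endpoint.** SAP 2.11 lists "Percent Change in Total Body Less Head (TBLH) Lean Body Mass obtained from the DXA scan at 3 Months", which matches the primary objective. SAP 2.10.1 is looser: "The absolute and percentage change in total body less head lean body mass at Visit 4 (Month 3) will be analyzed" by ANCOVA with baseline, treatment and country. It names no scan rule.
- **Population.** SAP 2.2 says of Intent-to-Treat: "Subjects will be analyzed as randomized, rather than as treated. This is the primary analysis population for assessing efficacy". Membership needs one dose, and subjects must "have a valid pre-baseline and post-baseline assessment will be included in the Intent-to-Treat population". There is no minimum exposure.
- **Reader.** SAP 2.10.2.1 makes the central reader's values primary and defines technical validity: "A valid DXA indicates the scan was acquired under the correct scanner setting, includes the entire region of interest and is free of artifacts".

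The scan rule is not settled. SAP 2.10.2.1 says that "there will be two definitions of a valid DXA for analysis purposes". The reason it offers is that dosing and scan timing varied in practice.

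- **Stringent:** at least 56 days on treatment, a valid baseline scan, and a scan within 14 days after stopping.
- **Liberal:** a valid baseline scan and any later scan before day 98.

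SAP 4.1 lists Intent-to-Treat, central-reader tables under both rules (14.2.01.1.1 stringent, 14.2.01.1.4 liberal). Figure 14.2.01.1 in SAP 4.2 names neither.

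Two other provisions bear on this. SAP 2.16 puts early-termination data into the Month 3 and Month 6 analyses, with data up to Day 112 going to Month 3. Protocol 6.10 and 7.7 require a DXA scan at early withdrawal.

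**The concern.** The scan rule decides who is in the primary analysis. With two rules and no ranking, the plan produces two candidate primary results.

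The stringent rule also depends on what happens after randomization. Staying on drug for 56 days, and being scanned soon after stopping, can both be affected by treatment or by how recovery goes. A comparison restricted this way describes subjects who remained on treatment, yet it would appear under an Intent-to-Treat label.

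Timing adds to this. SAP 2.11 says "The primary analysis will be performed in a partially unblinded fashion": results by actual treatment group become known at Month 3 while individual assignments stay masked. If the ranking is still open then, the version that leads the report can be chosen with the results in view.

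**Working it through.** **1. Is either rule designated primary?** SAP 2.10.1, 2.10.2.1, 2.11, 2.16 and the table list contain no designation. SAP 2.10.2.1 hints at the stringent rule: it is listed first, described as the initial concept, said to reflect a plan to exclude other subjects, and attributed to the protocol. The protocol text supplied has no 56-day or 14-day DXA rule in 6.10, 9.2 or 9.3.1. Protocol 6.10 refers to a study reference manual that was not supplied, so the source cannot be checked.

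**2. Who is treated differently?**

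| Subject | SAP 2.2 ITT | SAP 2.16 | Liberal | Stringent |
|---|---|---|---|---|
| Stops day 40, has the early-withdrawal scan | can qualify | Month 3 | in | out (under 56 days) |
| Stops day 60, only later scan is at day 84 | can qualify | on or before Day 112 | in | out (84 − 60 = 24 days off drug) |

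The first row is a direct contradiction between the stringent rule and SAP 2.16.

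**3. Upper day limits.** The liberal rule ends before day 98; SAP 2.16 uses Day 112. The stringent limit depends on the stopping day: 86 + 14 = 100 with Visit 4 at the end of its window (Protocol 7.7), or 90 + 14 = 104 at the 90-day limit (Protocol 2.7). So the stringent set is not strictly inside the liberal set. Only scans from day 98 to 104 are affected, and those would already be off schedule.

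**4. The plan's own figures.** The SAP 2.14 power statements reproduce at two-sided 0.05 (assumed, since the SAP states only a 95% interval). With 30 per arm and SD 1.3, noncentral t gives 83.4% and 99.2% against the stated 84% and 99%. With SD 2.0 and effects 1.6, 2.4 and 4.1, it gives 26, 16 and 7 per arm, as stated. The point does not rest on these figures.

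**5. Size of the gap (illustration).** SAP 2.14 projects 104 randomized and about 92 completing: 104/4 = 26 per arm, and (104 − 92)/4 = 3 lost per arm on average. Suppose *k* of 26 stop early but are scanned, and keep a fraction *r* of the full effect. The inclusive estimate is (26 − k + k·r)/26 of the full effect, and the stringent estimate is the full effect. Their ratio is 26/(26 − k + k·r), whatever the effect size.

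| k | r = 0 | r = 0.5 | r = 0.75 | r = 1 |
|---|---|---|---|---|
| 1 | 26/25 = +4.0% | 26/25.5 = +2.0% | 26/25.75 = +1.0% | 0 |
| 2 | 26/24 = +8.3% | 26/25 = +4.0% | 26/25.5 = +2.0% | 0 |
| 3 | 26/23 = +13.0% | 26/24.5 = +6.1% | 26/25.25 = +3.0% | 0 |

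**6. Power cost of the inclusive rule at 0.5 mg** (effect 1.6, SD 2.0, noncentral t, same *k* in both arms; inclusive uses n = 26 and the diluted effect, stringent uses n = 26 − k and the full effect).

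| k | r | Inclusive | Stringent |
|---|---|---|---|
| 1 | 0.5 | 79.2% | 79.1% |
| 1 | 0 | 77.6% | 79.1% |
| 3 | 0.5 | 76.0% | 75.6% |
| 3 | 0 | 70.6% | 75.6% |

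If early stoppers keep half the effect, including them costs no power. If they keep none, the cost is 1.5 points (k = 1) to 5.0 points (k = 3).

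**The case against.** **The stringent rule is primary by implication.** The hints in step 1 are real and narrow the gap. They do not close it: the exclusion is described as what was planned, the SAP then moves to two rules, and the protocol attribution cannot be confirmed. If the stringent rule is meant, its conflict with SAP 2.16 falls on the primary analysis itself.

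**A minimum-exposure rule can serve the objective.** The objective is efficacy after 12 weeks of treatment, so an on-treatment analysis is a legitimate question. That supports keeping it as a sensitivity analysis. The population named primary has no exposure minimum.

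**Safeguards exist.** The mid-study data review in SAP 2.14 was blinded, Protocol 5.6.2 withholds the randomization schedule from the statistician until database lock, and both versions are listed in advance. A reader might infer that the two rules were devised with knowledge of treatment, or that one result could be hidden. Nothing in the documents shows the first, and the table list rules out the second.

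**As-randomized analysis is not breached.** A reader might infer that the stringent rule violates the statement in SAP 2.2 that subjects are analysed as randomized. That statement governs which arm a subject is counted in, and the stringent rule leaves it intact. The sound argument is the conflict with SAP 2.16.

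**The Day 112 sentence may be narrow.** It directly follows the sentence on early-termination visits and may apply only to those data. The limits still need reconciling, but the mismatch is mostly an edge case.

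**Conclusion.** The concern holds as a gap in the specification of the primary analysis, together with a direct contradiction between the stringent rule and SAP 2.16. It should be fixed before the Month 3 unblinding. The finding rests on the text and does not depend on the illustrative numbers.

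The size is probably modest: about 1–13% on the estimate for 1 to 3 early stoppers per arm keeping 0–75% of the effect, and nothing at full retention. The top of the range assumes no effect retained, which is extreme because Protocol 5.3 reports a lean-mass increase in a 21-day study, albeit in healthy men.

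Two stronger readings are not supported. Three per arm should not be taken as a bound: it is a planning average, a single arm could lose more, and the 14-day condition can also exclude subjects treated beyond 56 days. Nor is the range an estimate of bias. It shows dilution only; the direction and size of any selection effect cannot be worked out from the documents.

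**What to change.** Before the Month 3 unblinding:

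1. In SAP 2.10.1, name one primary analysis: Intent-to-Treat, central reader, ANCOVA on percent change in total-body-less-head lean mass. Use every subject with a technically valid baseline scan and a technically valid post-baseline Month 3 or early-termination scan, regardless of days on treatment.
2. Use one upper day limit in both 2.10.2.1 and 2.16. The Day 112 already in 2.16 would serve, and it covers every scan in step 3.
3. Keep the stringent rule as a labelled sensitivity analysis, and either cite its source or correct the attribution to the protocol.
4. Apply the technical definition of a valid scan to DXA endpoints only. Leave Intent-to-Treat membership for other endpoints unchanged; otherwise subjects with usable walk-test, SPPB, SF-36 or bone-marker data would be lost from those tables.
5. Name the scan rule in the title of Figure 14.2.01.1.

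The cost is a few SAP sentences and no new data. The headline effect may be slightly smaller, and some scans will reflect short exposure, which the stringent sensitivity analysis addresses.

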2.9 Early Termination

In case of early termination, the events will be performed according to [Table 1](#) and will be identical to Visit 4, excluding plasma concentration sample collection.

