6.10 DXA Scans

DXA scans will be performed at Randomization and at Visits 4 and 5, or in case of early withdrawal as shown in [Table 1](#). Instructions for DXA scans are provided in the study reference manual.

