6.12 Plasma Concentration Sample Collection

Blood samples to determine plasma study drug concentration will be collected at Visits 2, 3, 4 and 5 as shown in [Table 1](#).

Pre-dose samples will be collected on the appropriate days at 0 to 20 min pre-dose (Visits 2, 3, and 4). A single post-dose sample will be collected thereafter at 2 hours (\pm 10 min) post-dose (Visits 2, 3, and 4), plus one additional sample at Visit 5.

At each collection, 5 mL of blood will be collected into a Vacutainer tube containing lithium heparin (green top) and immediately placed in an ice bath. Within 30 minutes of collection, the plasma fraction will be separated by centrifugation at 2,500 rpm (1,000 x g) for 15 minutes at 4°C. The plasma fraction will be separated into equal aliquots and transferred into 2 labeled 5 mL polypropylene tubes and frozen at approximately -20°C or -70°C.

Blood volume collected for these samples will be approximately 20 mL total per subject.

Plasma concentration samples should be shipped on dry ice via overnight delivery to MicroConstants for analysis. Samples will ship only on a Monday, Tuesday or Wednesday to minimize the possibility of the samples being in transit over a weekend. Duplicate plasma concentration samples will ship after MicroConstants confirms receipt of the initial samples.

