2.10.2.2. Plasma Concentration Analysis

Pre-dose and single post-dose plasma concentrations of VK5211 at Visits 2, 3 and 4 and the single plasma concentration at Visit 5 will be summarized using mean, geometric mean, standard deviation, coefficient of variation (CV%), median, minimum and maximum.

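### Correlating concentration with lean mass over all post-baseline visits combined mixes on-drug and off-drug records, so it can show a spurious exposure-response whenever mean lean mass change differs between Visits 4 and 5

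*SAP*

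**What the plan says.** The relation of plasma concentration near Tmax and at trough to total lean body mass is a secondary objective (Protocol 3.2, SAP 1.3.2). For this, SAP 2.10.2.1 plans correlations and regression lines, for observed values and for change from baseline, which "will also be analyzed for each VK5211 treatment group and all VK5211 treatment groups combined". It continues: "This analysis will be performed by visit and for all post-baseline visits combined". No visit term, repeated-measures structure or pairing rule is given. Placebo is not part of the correlation.

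The sampling schedule limits what can be paired:

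- Lean mass (Protocol 6.10): "DXA scans will be performed at Randomization and at Visits 4 and 5, or in case of early withdrawal".
- Concentration (Protocol 6.12): "Blood samples to determine plasma study drug concentration will be collected at Visits 2, 3, 4 and 5". Visits 2 to 4 have a pre-dose and a 2-hour sample, "plus one additional sample at Visit 5". SAP 2.10.2.2 says that "the single plasma concentration at Visit 5 will be summarized".
- Early termination (Protocol 2.9): assessments are "identical to Visit 4, excluding plasma concentration sample collection".

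Protocol 9.4 asks only that the correlations be derived and shown graphically. It does not mention pooling over visits; that appears in the SAP.

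**The concern.** Same-visit pairs of concentration and lean mass exist only at Visit 4 and Visit 5. Visit 5 is scheduled for Day 168 and Visit 4 for Day 84, so Visit 5 falls 168 − 84 = 84 days (12 weeks) after dosing ends. Pooling the two visits produces one cluster of points at on-treatment concentrations and another near zero. The fitted line mostly joins the two cluster means. Its slope reflects how lean mass changed between the visits, from loss of drug effect, natural recovery or further decline. It does not show whether treated subjects with higher concentrations gained more.

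Protocol 5.3 says the trial is meant to establish the optimal dose for further development, and the exposure-response result bears on that. A pooled r and regression line in Table and Figure 14.2.05 could be read as a concentration gradient among treated subjects when there is none.

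**Working it through.** **1. Inputs and the plan's own figures.** The documents give no figure for this correlation, so effect, SD and sample size are taken from SAP 2.14. Those figures reproduce. With 30 per group and SD 1.3, a two-sided 5% t-test has 83.4% power for 1.0 kg and 99.3% for 1.5 kg (84.6% and 99.4% by normal approximation), against the stated 84% and 99%. With SD 2.0, effects of 1.6, 2.4 and 4.1 need 25.5, 15.6 and 6.1 per group, which round up to the stated 26, 16 and 7. The illustration uses the revised set: effects 1.6, 2.4 and 4.1 (units not stated), SD 2.0, about 23 completers per group.

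**2. Assumptions not in the documents.** Visit 5 concentration is zero. On-drug concentration is log-normal with CV 40%. A subject's two changes from baseline correlate 0.5. The fraction of the Month 3 gain kept at Visit 5 runs from 100% to 0%. Within any visit and dose, concentration and lean mass change are unrelated.

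**3. Expected pooled correlation in one dose group.** Let Δ be mean change at Visit 4 minus mean change at Visit 5, and μ the mean on-drug concentration. With equal numbers of records at each visit:

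- covariance = (μ/2)(Δ/2) = μΔ/4
- variance of concentration = μ²(1/4 + CV²/2) = μ²(0.25 + 0.08) = 0.33μ²
- variance of change = SD² + Δ²/4
- r = (Δ/4) / √[0.33 × (SD² + Δ²/4)]

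Effect 4.1, half kept: Δ = 2.05, so r = 0.5125 / √(0.33 × 5.05) = 0.40. None kept: Δ = 4.1, so r = 1.025 / √(0.33 × 8.20) = 0.62. If Δ = 0, r = 0. If Δ is negative, so is r.

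**4. Simulation** (3,000 to 5,000 trials per case, Pearson correlation, Visit 4 and Visit 5 rows treated as independent). Mean r agrees with the formula to within about 0.015. Repeat runs move the percentages by up to about 2 points.

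| Gain kept at Visit 5 | Mean r, effect 1.6 / 2.4 / 4.1 | p<0.05, effect 1.6 / 2.4 / 4.1 |
|---|---|---|
| 100% | 0 / 0 / 0 | 1–2% each |
| 75% | 0.09 / 0.14 / 0.22 | 4% / 9% / 28% |
| 50% | 0.18 / 0.26 / 0.41 | 17% / 38% / 89% |
| 0% | 0.33 / 0.46 / 0.64 | 66% / 95% / 100% |
| Visit 4 alone, any row | about 0 | about 5% |

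**5. Variations.**

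- Pre-study inputs (0.5, 1.0 and 1.5 kg, SD 1.3, 30 per group): p<0.05 in 6%, 19% and 48% with half kept, and in 20%, 77% and 99% with none kept.
- All doses combined, the same effect of 2.4 at every dose: about 72% with half kept.
- All doses combined, no drug effect at all, mean change 1.0 lower at Visit 5: r about 0.18, p<0.05 in about 55%. If it is 1.0 higher at Visit 5: r about −0.18, also about 55%.
- Concentration CV from 20% to 70%, at Δ = 1.6: 78% down to 49%.
- Observed lean mass instead of change (assumed between-subject SD 6 to 10 kg): 0.1–1.3% at Δ = 1.6, 1–6% at 2.4, 8–47% at 4.1.

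**The case against.** A reader might infer that the pooled analysis will yield a significant correlation where no exposure-response exists. The documents do not support that, for these reasons:

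- **The bias is conditional.** It needs mean lean mass change to differ between the visits. No document says how much gain is lost by Visit 5; the follow-up is there partly to find out. If the gain is kept, the pooled test is conservative (1–2%), so treating two records per subject as independent does not inflate error in that case. The SAP 2.14 effects are placebo-adjusted, whereas Δ is a within-arm change that also includes natural recovery.
- **No test is named.** The text specifies correlations and regression lines without a p-value or decision rule, and the table shells are in a separate file. The percentages with p<0.05 show the size of the bias; they are not error rates of a planned test.
- **Pairing Visit 4 with Visit 5 is one reading.** The Visit 5 sample is not tied to a dose, so it is neither trough nor near Tmax. Read strictly, Visit 5 drops out. Pairing Visit 2 and 3 concentrations with the Month 3 scan is not excluded either.
- **A fading real effect is not nothing.** The pooled line then shows drug against no drug. The mistake would be to read it as a concentration gradient among treated subjects.
- **The Visit 4 result will also exist**, since a by-visit analysis is planned.

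All of this stands, and it limits how strongly the point can be put. It does not rescue the pooled sentence. Without Visit 5 the combined analysis repeats Visit 4, and with Visit 2 and 3 concentrations it counts one lean mass outcome up to three times per subject. The SAP also gives the by-visit result no priority if the two disagree.

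**Conclusion.** The point holds in conditional form. Paired within visit, the pooled change-from-baseline analysis confounds concentration with visit and can show a false exposure-response of either sign whenever mean change differs between Visits 4 and 5. With half the gain kept, the bias in r ranges from about 0.18 (effect 1.6) to 0.41 (effect 4.1). It vanishes if all the gain is kept and is absent from the Visit 4 analysis. For observed values it is much smaller, except at the largest shift.

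These sizes rest on the assumed zero concentration at Visit 5, 40% CV, within-subject correlation of 0.5 and retained fraction. The structural point rests on the visit schedule alone. Because no test is specified, the main harm is a misleading coefficient and line in Table and Figure 14.2.05. The correction is worth making because the analysis serves a stated secondary objective and no reading makes the simple pooled version informative.

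**What to change.** In SAP 2.10.2.1:

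1. Name Visit 4 as the exposure-response analysis: trough and near-Tmax concentration at Visit 4 against Month 3 change in total lean body mass, one record per subject, by dose and for all doses combined.
2. Delete the simple pooled analysis, or replace it with a model that has a visit term and a subject effect.
3. State that the Visit 5 sample is neither trough nor near Tmax and is summarised separately, as SAP 2.10.2.2 already provides.

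The change takes a few lines of SAP text and needs no new data. The cost is small but not nil: one pooled table and figure panel is lost, or a slightly more complex model takes its place. Visit 5 lean mass remains in the Month 6 DXA analyses, so the information on duration of effect is kept.
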